## $H_0: \lambda \geq 2 \cdot OPC$

## $H_A: \lambda < 2 \cdot OPC$

This document and the information contained herein is considered Proprietary and Confidential and may not be reproduced, used or disclosed without written permission from Edwards Lifesciences LLC.

where  $\lambda$  is the linearized rate for the given adverse event (thromboembolism, valve thrombosis, all hemorrhage, all perivalvular leak, and endocarditis) computed when the total subject years reaches 808 and *OPC* denotes the relevant OPC. The test statistic for each adverse event is of the form:

$$Z = (\lambda - 2 \cdot OPC) / \sqrt{\lambda} .$$

 $H_0$  is rejected in favor of  $H_A$  if Z is less than -1.645, the lower 5% percentile of the standard normal distribution. Grunkemeier, et al. have demonstrated that 800 subject life-years is adequate to test against the smallest OPC of 1.2% per subject year (excluding valve thrombosis, and stratification for major versus minor hemorrhage, and perivalvular leak) with Type I and Type II error controlled at the .05 and .20 levels, respectively.

The proposed subject enrollment is calculated to ensure that at least 101 subjects survive to 8 years post implant. These 8\*101 = 808 life years in addition to the life years from those subjects not surviving to 8 years will more than fulfill the 800 life-years required by Grunkemeier, et al..

Sample size calculation for primary effectiveness endpoint is based on a test of the hypothesis:

 $H_0: p \le 75\%$  $H_A: p > 75\%$ 

where *p* is the proportion of the subjects in NYHA Class I or Class II at 8 years post implant. The expected proportion of the alive subjects in NYHA class I or II at eight years is approximately 90%, based on 7 year follow up data for the Carpentier-Edwards PERIMOUNT 6900/6900P valve (this proportion is essentially constant across each annual visit). Based on this expected proportion, a sample size of 45 subjects provides 85% power to test the hypothesis that the true proportion is greater than 75% using an exact binomial test. Thus, the sample size of 101 subjects with NYHA data at 8 year post implant is more than adequate to provide sufficient power.

This document and the information contained herein is considered Proprietary and Confidential and may not be reproduced, used or disclosed without written permission from Edwards Lifesciences LLC.

The calculated number of subjects (n) that must be enrolled in order to have 101 subjects survive to 8 years post implant with 99% probability is based on the binomial distribution. Specifically, n is such that

$$1 - \sum_{x=1}^{101} {n \choose x} p^x (1-p)^{n-x} > 98.7\%$$

where *p* is the probability that a subject will survive for 8 years post implant. This calculation can be performed using standard statistical software. Based on the reported 8-year survival of 56% from Thourani, et al. , a sample size of 212 subjects fulfills the requirements of the equation above. Based on the data collected in a previous post approval study conducted by Edwards (Study 98-1), a lost to follow-up rate of 7.8% was observed among subjects who reached 5 or more years of follow-up post implant. The sample size is further inflated to 250 to account for up to a 15% rate of lost to follow up.

The STS Executive Summary indicated that 15% of patients undergoing mitral valve surgery in 2007 in the United States underwent simultaneous mitral and aortic valve replacement (1205/7883). In order to reflect actual market use of the Carpentier-Edwards PERIMOUNT Magna Mitral valve, of the 250 subjects enrolled in the study, approximately 38 are anticipated to be those patients eligible for simultaneous aortic and mitral valve replacement.

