## 9.1 Sample Size Calculation

The sample size calculation for the trial is based on the primary safety endpoints. The linearized rates for thromboembolism, all hemorrhage, all perivalvular leak, and endocarditis will be compared to the Objective Performance Criteria from Annex R, Table R.1 per ISO 5840 as proposed by the US FDA in the Heart Valve Guidance draft 2009. These OPC are presented in Table 11.

Adverse Event	OPC
Thromboembolism	2.5
All Hemorrhage	1.4
All Perivalvular Leak	1.2
Endocarditis	1.2

Table 11: Safety OPC

More specifically, a statistical test based on the Poisson distribution will be performed for each of these adverse event rates to evaluate whether it is less than 2 times the appropriate OPC. Thus, the null and alternative hypotheses for each adverse event are as follows:

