## 9.3 Safety Analysis

## 9.3.1 Primary Safety Endpoint

As described above a statistical test based on the Poisson distribution will be performed to investigate whether the linearized yearly rate for each

This document and the information contained herein is considered Proprietary and Confidential and may not be reproduced, used or disclosed without written permission from Edwards Lifesciences LLC.

cardiovascular adverse event (thromboembolism, all hemorrhage, all perivalvular leak, and endocarditis) is less than 2 times the appropriate Objective Performance Criteria from Annex R, Table R.1 per ISO 5840 as proposed by the US FDA in the Heart Valve Guidance draft 2009.

For reporting purposes, the percent of subjects who experience an early adverse events within 30 days of implant will be summarized. Linearized rates will be used to summarize adverse events for the late (>30 days) post-operative period. The linearized rates will be reported as the number of events occurring after the early post-operative period per year of subject survival. In addition, the linearized rate and 30-day frequency for thromboembolism will be stratified by concomitant cardiac problems (atrial fibrillation, sinus rhythm, pacemakers, etc.).

Accounting for both early and late post-operative events, actuarial analysis according to Kaplan-Meier will be used to show estimated probability of freedom from each adverse event.

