	Myocardial Infarction		Peri-operative Myocardial Infarction (MI) (0-24 hours post-op) as documented by the following criteria: The CK-MB (or CK if MB not available) must be ≥5 times the upper limit of normal, with or without new Q waves present in two or more contiguous ECG leads. No symptoms required. Peri-operative Myocardial Infarction (MI) (> 24 hours post-op) as documented by at least one of the following criteria:1. Evolutionary ST-segment elevations, 2. Development of new Q- waves in two or more contiguous ECG leads, 3. New or presumably new LBBB pattern on the ECG, CK4. The CK-MB (or CK if MB not available) must be greater than or equal to 3 times the upper limit of Normal.	Not defined
Embolic Events				
	Embolism	General Def	An embolism is a free flowing blood clot or lesion material that is located in the systemic or pulmonary circulation that occurs in the absence of infection after immediate perioperative period. May be manifested as neurological event or non-cerebral embolic event. Non-cerebral event is an embolus documented operatively, autopsy or clinically that produces signs and symptoms attributable to partial or complete obstruction of a peripheral artery. Excludes post-operative MI unless detected by operation, clinical imaging or autopsy, emboli caused by non-thrombotic material (atherosclerosis, myxoma).	Not defined
	Thromboembol ism		The combination of thrombosis and its main complication, embolism. Thrombosis is the formation of a blood clot inside a blood vessel, obstructing the flow of blood through the circulartory system	Not defined

	Thrombotic obstruction		Obstruction by thrombus formation	Not defined
	Peripheral Embolic Event		A peripheral embolic event is an operative, autopsy, or clinically documented embolus that produces symptoms from complete or partial obstruction of a peripheral (noncerebral) artery. Report under Pulmonary Embolism if event occurs in the lung.	Not defined
		Specify location:		
	Pulmonary Embolism		Clinical evidence of new embolism with confirmation by lung scan or pulmonary angiography.	Event that occurs within 90 days of the index procedure will be considered procedure related .
	Stroke		Prolonged (> 72 hrs) or permanent neurological deficit that is usually associated with abnormal results of MRI or CT scans. Patients with minimal, atypical, or protean symptoms that lead to radiographic imaging demonstrating an acute ischemic event are considered to have a stroke.	Not defined

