	Moderate	Qualitative: angiographic grade 2+; Color Doppler jet area- signs of MR greater than Mild present but no criteria for Sever Mr; Doppler vena contracta width (cm) 0.3-69. Quantitative (cath or echo):Regurgitant volume (ml/beat) 30-59;Regurgitant fraction (%) 30-49; Regurgitant orifice area (cm2) 0.20-0.39.	
	Severe	Qualitative: angiographic grade3-4+; Color Doppler jet area- Vena contracta width > 0.7 with large central MR jet (area > 40% of LA area) or with a wall-impinging jetof any size, swirling in LA; Doppler Vena contracta width > 0.7. Quantitative (cath or echo):Regurgitant volume (ml/beat) >/=60;Regurgitant fraction (%) >/=50; Regurgitant orifice area (cm2) >/=0.40.	
Tricuspid Stenosis		A narrowing of the tricuspid valve opening that increases resistance to blood flow from the right atrium to the right ventricle. Severe tricuspid stenosis is defined as a valve area less than 1.0 cm2.	
Tricuspid Regurgitation		Insufficiency of the tricuspid valve causing blood flow from the right ventricle to the right atrium during systole. Severe regurgitation characterized by Vena contracta width greater than 0.7 cm and Systolic flow reversal in hepatic veins.	
Other Valve, specify location:		Other valve (e.g. pulmonic) valve disease or deterioration reported after the AVR procedure.	
Structural Deterioration		Includes dysfunction or deterioration involving the replacement heart valve (exclusive of infection or thrombosis) determined by reoperation, autopsy or clinical investigation. Refers to changes intrinsic to the valve such as wear, fracture, leaflet escape, calcification, leaflet tear, stent creep, suture line disruption of components of prosthetic valve, new chordal rupture, leaflet disruption, or leaflet retraction of repaired valve.	By definition all are valve related .
	Calcification		
	Leaflet tear		
	Stress Fracture		
	Stent creep		
	Suture line disruption		
	vvear damage		
	Loss of structural integrity	Loss of structural integrity of metallic valve component such as wireform, frame, etc.	

		Other Structural		
		Deterioration,		
		specify:		
Valvular	Non Structural		Any abnormality not intrinsic to the valve itself that results in stenosis or regurgitation	
Valvalai	Dysfunction		of the replacement heart valve. Refers to problems (exclusive of thrombosis and	
	Dyoranotion		infection) that do not directly involve valve components yet result in dysfunction as	

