			diagnosed by reoperation, autopsy or clinical investigation. E.g. Entrapment by	
			pannus, tissue or suture. PV leak, inappropriate sizing or positioning, residual leak or	
			obstruction after valve implantation or repair, regurgitation due to technical errors,	
			dilatation of the sinotubular junction, dilatation of the valve annulus. In AVR	
			percutaneous approaches: new onset of coronary ischemia from ostial obstruction or	
			PV aortic regurgitation.	
		Annulus		
		dilatation		
		Entrapment-		
		leaflet		
		Specify leaflet		
		Entrapment-		
		pannus		
		Inappropriate		
		Sizing		
		Inappropriate		
		Positioning		
		Ostial		
		obstruction		
		Perivalvular	Clinically or haemodynamically detectable defect between the heart valve substitute	
		Leak	and the patient's annulus.	
		Major	1. PAL requiring surgical re intervention, and; 2. PVL requiring	
			medical intervention only (i.e., after load reduction, occasional blood transfusion for	
			mild Hemolysis).	
		Minor	1. Evidence of AI by echo without symptoms and with no Hemolysis that does not	
			require any intervention.	
			2. Presence of non-taminar now without symptoms and with no nemotysis that does	
	 		not require any intervention and requires monitoring.	
		Valve	Blood clot, not associated with infection, causing dysfunction of the heart valve	
		Inrombosis	substitute. Diagnosis confirmed by echocardiography, anglocardiography or magnetic	
			resonance imaging, operation, explant, or autopsy.	
	1			1

		Other Non Structural Dysfunction, specify	Other structural dysfunction not defined above.	
Other Events				
	Allergic Reaction		Hypersensitivity to an allergen such as a medication, contrast agent, food or airborne substance. The reaction can be characterized by rash, nausea, vomiting, upper respiratory congestion, urticaria, shortness-of-breath, vasovagal reaction, or general collapse (anaphylaxis) Specific Allergen should be reported if known.	Not defined
	Esophageal Injury		Any evidence of puncture/dissection/perforation, varices or other damage to the esophagus requiring intervention	Not defined

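### Section 9.1 lists valve thrombosis among the events tested against twice the OPC but gives no OPC for it, and Appendix 8 files it under nonstructural dysfunction, whose definition excludes it

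*Combined protocol and SAP*

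**What the plan says.** **Primary safety tests.** Section 9.1 opens with four events: "The linearized rates for thromboembolism, all hemorrhage, all perivalvular leak, and endocarditis will be compared to the Objective Performance Criteria". It then points to the thresholds: "These OPC are presented in Table 11". That table has four rows: thromboembolism 2.5, all hemorrhage 1.4, all perivalvular leak 1.2 and endocarditis 1.2. Below the hypotheses, the paragraph that fixes the rate, the test statistic and the rejection rule lists five: "thromboembolism, valve thrombosis, all hemorrhage, all perivalvular leak, and endocarditis". A few lines later it says that the 800 patient-year requirement was set leaving valve thrombosis aside. Section 9.3.1, which governs the analysis, returns to four: "thromboembolism, all hemorrhage, all perivalvular leak, and endocarditis) is less than 2 times the appropriate Objective Performance Criteria". The synopsis and 3.3.1 list the same four. Section 3.3.2 lists valve thrombosis as a secondary safety endpoint, separate from non-structural valve dysfunction.

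**Event coding.** The Non Structural Dysfunction entry in Appendix 8 reads "Refers to problems (exclusive of thrombosis and" and goes on to exclude infection as well. Among its subcategories, between the perivalvular leak rows and the residual row for other nonstructural dysfunction, stands Valve Thrombosis: "Blood clot, not associated with infection, causing dysfunction of the heart valve". Under Embolic Events there is also a Thrombotic obstruction row, defined only as "Obstruction by thrombus formation". Section 6.1.2 has events assessed by the Appendix 1 guideline but reported by the Appendix 8 classification. Appendix 1 gives valve thrombosis its own heading and excludes it from nonstructural dysfunction.

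**The concern.** The paragraph in 9.1 is the only place where hypothesis, statistic and critical value are written out together, and it names an event for which the threshold does not exist in the plan. Anyone programming from that paragraph must either drop an event or find an OPC elsewhere, and the number of primary safety hypotheses should not be settled after the data are in.

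The Appendix 8 entry matters because reporting follows that appendix. A clot on the study valve, coded by the listing, would enter the nonstructural dysfunction rate of 9.4.3, although the category definition, Appendix 1 and 3.3.2 all keep the two apart. The Thrombotic obstruction row is loose enough that an obstructive clot on the study valve could also be coded there. At stake are two secondary rates, not a primary conclusion.

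**Working it through.** **1. Which events have a threshold.**

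| Place | Events named for the OPC comparison | Valve thrombosis |
|---|---|---|
| Synopsis | 4 | secondary |
| 3.3.1 / 3.3.2 | 4 | secondary (3.3.2) |
| 9.1, opening | 4 | not named |
| Table 11 | 4 OPCs | no row |
| 9.1, below the hypotheses | 5 | named |
| 9.1, sizing sentence | smallest OPC 1.2 | excluded |
| 9.3.1 | 4 | not named |

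One place out of seven includes it, and the sizing sentence in that same paragraph leaves it out.

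**2. Does the stated sizing depend on the fifth event?** Take the plan's inputs: OPC 1.2 per 100 patient-years, null boundary 2 × OPC, true rate equal to the OPC, one-sided 5%, power 80%. At 800 patient-years the null mean is 2 × 0.012 × 800 = 19.2 events and the alternative mean is 9.6. The largest count c with P(X ≤ c | 19.2) ≤ 0.05 is 11 (probability 0.032), and P(X ≤ 11 | 9.6) = 0.741. Exact power first reaches 0.80 at 811 patient-years, which is 1.4% above 800. Because counts are discrete, it stays at or above 0.80 only from 912. The normal approximation with null and alternative variances gives 0.780 at 800. So the stated figure is reproduced approximately from the smallest of the four Table 11 values, and valve thrombosis plays no part in it. Removing the term leaves the sizing as it was.

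**3. Can the fifth test be run?** The statistic is Z = (λ − 2·OPC)/√λ. Without an OPC the numerator is unknown. With zero events, λ = 0 and the denominator is √0, so Z is undefined whatever OPC is used. Zero is a plausible outcome: the predecessor tables show 0 early and 0 late thromboses for model 6900 (1,100 patient-years) and the same for model 6900P (873.18 patient-years).

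**4. How large could the coding effect be?** Combined predecessor exposure is 1,100 + 873.18 = 1,973.18 patient-years with no events. The one-sided 95% upper Poisson limit is −ln(0.05)/1,973.18 = 2.996/1,973.18 = 0.152 per 100 patient-years. Over 808 patient-years that is at most 0.00152 × 808 = 1.2 expected events, assuming a constant rate that carries over to the study valves. Each event coded as nonstructural dysfunction adds 1/808 = 0.12 per 100 patient-years to that rate. For scale, the predecessor late nonstructural rates are 3/1,072.5 = 0.28 and 1/856.24 = 0.12 per 100 patient-years. The expected shift is small, but a single misfiled event would be noticeable against so low a base.

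**5. The Appendix 8 definitions side by side.** The category excludes thrombosis; the subcategory is a non-infective clot that impairs the valve. No event can satisfy both. Section 9.4.3 does not say whether the definition or the listing decides what enters the overall rate.

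**The case against.** The strongest reply is that this is a stray word. Four events, each with an OPC, are stated consistently in the synopsis, 3.3.1, the opening of 9.1 and 9.3.1, and the hypotheses in 9.1 are introduced as applying to the events just tabulated. A careful reader would run four tests. That stands, and it is why the primary analysis is not in doubt.

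A reader might go further and infer a live fifth primary hypothesis that is badly underpowered against the stated 80%. The documents do not support this. No OPC is given, so any power figure would rest on an invented threshold, and the error rates in 9.1 are stated with valve thrombosis set aside. The wording of the sizing sentence suggests that the cited source has a smaller value for valve thrombosis, but the plan does not reproduce one.

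A reader might also object that Appendix 8 places perivalvular leak under nonstructural dysfunction and so inflates that rate. That is not a defect: Appendix 1 gives paravalvular leak as an example of nonstructural dysfunction. Section 9.4.3 splits the rate by type of dysfunction, and 3.3.2 reports leak separately.

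The same split in 9.4.3 would let a thrombosis be separated out afterwards. This limits the harm but does not settle whether the overall rate includes it. Finally, the Appendix 8 layout should be read with care, since major and minor leak sit at the same depth as their parent row. The placement of Valve Thrombosis before the residual row for other nonstructural dysfunction still puts it inside that block.

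**Conclusion.** Both contradictions are real and limited in reach. The list below the hypotheses in 9.1 cannot be executed for valve thrombosis, because the plan supplies no OPC and the stated Z is undefined at zero events. The primary safety analysis remains four tests with four thresholds, and the 800 patient-year basis does not change. In Appendix 8 the listing contradicts the category definition, 3.3.2 and Appendix 1, so it is open whether valve thromboses enter the nonstructural dysfunction rate.

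The likely numerical effect is small: no thromboses in either predecessor series, and about 0.12 per 100 patient-years for each misfiled event at 808 patient-years, less if exposure is larger. This assumes that the predecessor experience carries over to the study valves. Double coding through Thrombotic obstruction is possible under the wording, but nothing in the documents shows that it has happened. The correction is worth making before the final analysis because it removes a choice that would otherwise be made with the data in hand.

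**What to change.** - **Section 9.1:** delete valve thrombosis from the list that defines λ, so that it matches Table 11 and 9.3.1.
- **Secondary analysis:** report valve thrombosis as a secondary linearized rate with an exact Poisson interval. Unlike Z, this is defined at zero events: with none in 808 patient-years the two-sided 95% upper limit is −ln(0.025)/808 = 3.689/808 = 0.46 per 100 patient-years.
- **Appendix 8:** make Valve Thrombosis its own event name outside Non Structural Dysfunction, and direct thrombotic obstruction of the study valve to it.
- **Section 9.4.3:** state that the nonstructural dysfunction rate excludes valve thrombosis.

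The cost is wording in three places and recoding of any thrombosis already reported; 249 patients had a study valve in place at discharge by November 2013, so accrued reports need checking. Section 10.7 requires protocol changes to be agreed with the FDA and then approved by the IRB or ethics committee, unless they qualify as administrative. No new data, visits or subjects are needed.

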#### 3.3 Endpoints

#### 3.3.1 Primary Safety Endpoints

Long term safety performance will be evaluated by comparing the linearized rates listed below to the objective performance criteria referenced in ISO 5840-2005, Cardiovascular Implants-Cardiac Valve Prostheses

- Thromboembolism
- All Hemorrhage
- All Perivalvular Leak
- Endocarditis

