#### **Table 2: Revised Study Reporting Time**

#### Justification for Change in the Study Reporting Time

As of November 4, 2013, a total of 249 patients had a study valve in place at discharge. Therefore, only one (1) additional subject must be implanted between now and December 31, 2014, to meet the protocol requirement of 250 subjects implanted. Of the minimum 250 implanted subjects required per revision H of study protocol (2006-05), a minimum of 101 subjects must be followed for eight (8) years. As of November 4, 2013, we have lost the ability to follow 55 patients either due to death, withdrawal or removal of the study valve. This leaves 203 who can potentially make it to the eight (8) year follow up. Currently, the longest recorded follow-up is five (5) years. Therefore, it will be another three (3) years before the first patient reaches the 8-year follow-up visit and up to six (6) years to achieve 101 patients with eight (8)

This document and the information contained herein is considered Proprietary and Confidential and may not be reproduced, used or disclosed without written permission from Edwards Lifesciences LLC.

year follow-up data. As a result, Edwards anticipates the **final study report** will be submitted in December 2020.

Location	Protocol Revision	Revision Date	Valve Model No(s).
United States/Europe (Not implemented)	Revision A	January 23, 2007	7000/7000TFX
Europe	Revision B.	May 23, 2007	7000/7000TFX
United States/Europe (Not implemented)	Revision C	July 17, 2007	7000/7000TFX
United States/Europe	Revision D	September 25, 2008	7000/7000TFX
United States/Europe	Revision E	January 23, 2009	7000/7000TFX
United States (Northwestern University only)	Revision F	November 24, 2009	7200TFX
United States (Not implemented)	Revision G	September 17, 2010	7300/7300TFX
United States/Europe	Revision H	May 24, 2011	7000/7000TFX/ 7300/7300TFX

Table 3. Study Enrollment by Protocol Revision by Valve Model

Edwards continues to actively review study recruitment procedures in an ongoing effort to improve study enrollment rates and complete the study in a timely fashion.

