## 9.2 Analysis Population

All the data collected up to the point of the explant or expirations will be included in the safety and effectiveness analyses. The primary safety analysis will include all the enrolled subjects. The primary effectiveness analysis will include the subjects who survived and have NYHA assessment at 8 years post implant.

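### The primary safety rates are timed to 808 total subject-years, but 808 is the exposure of the 8-year survivors alone

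*Combined protocol and SAP*

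**What the plan says.** Section 9.1 (Sample Size Calculation) tests each of the four primary event rates against twice its OPC and defines the tested rate as the one "computed when the total subject years reaches 808". Later in the section, enrolment is sized so that "at least 101 subjects survive to 8 years post implant". The product 8 × 101 = 808 is then formed, and these "life years in addition to the life years from those subjects not surviving to 8 years will more than fulfill the 800 life-years required" by the cited sample-size paper.

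Section 9.2 (Analysis Population) states: "All the data collected up to the point of the explant or expirations will be included in the safety and effectiveness analyses". It adds: "The primary safety analysis will include all the enrolled subjects".

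Section 9.3.1 takes the test over from 9.1 ("As described above a statistical test based on the Poisson distribution will be performed") and sets no data cut of its own. Section 3.3.1 presents the endpoint as long-term: "Long term safety performance will be evaluated by comparing the linearized rates listed below". Table 2 in Section 4.2 ties the final report, due 31 December 2020, to at least 101 patients having 8-year follow-up. No report is tied to a subject-year total.

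**The concern.** Within Section 9.1, 808 is the total exposure in one sentence and only the survivors' part of the total in another. Both hold only if everyone who dies, withdraws or is explanted before 8 years contributes nothing. Because 9.3.1 refers back to 9.1, the 808 trigger is the only explicit data cut for the four primary tests.

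An analyst who follows it would compute the rates as soon as pooled follow-up reaches 808 years. One who follows 9.2 and Table 2 would wait for the final data. They would report different primary rates, from different dates and different amounts of follow-up. With annual interim reports running throughout, the choice between them could be made after rates have been seen.

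**Working it through.** **The plan's own figures.** 8 × 101 = 808. With 8-year survival 56% and n = 212, the binomial probability of more than 101 survivors is 99.1%, above the 98.7% in the formula. 212/0.85 = 249.4, rounded up to 250. All reproduce.

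**Expected exposure to 8 years.** The plan gives no total, so it is built here on assumptions:
- n = 250 implanted (Section 4.0).
- 8-year retention R: 0.56 (Section 9.1 survival, no loss to follow-up); 0.56 × 0.85 = 0.476 (with the 15% allowance); or 101/250 = 0.404 (target just met).
- Early deaths e: 0, or 9.4% (model 6900, Table 1 of the 7000TFX instructions for use).
- Constant hazard thereafter, exposure capped at 8 years.

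h = −ln[R/(1−e)]/8 and E = n(1−e)(1−exp(−8h))/h.

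| R | e | E (subject-years) | Beyond 808 |
|---|---|---|---|
| 0.56 | 0 | 1,518 | 46.8% |
| 0.56 | 9.4% | 1,438 | 43.8% |
| 0.476 | 0 | 1,412 | 42.8% |
| 0.476 | 9.4% | 1,336 | 39.5% |
| 0.404 | 0 | 1,315 | 38.6% |
| 0.404 | 9.4% | 1,243 | 35.0% |

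Example: 1 − 808/1,518 = 46.8%. As a sensitivity check, linear decline with e = 0 gives 250 × 8(1+R)/2 = 1,404 to 1,560, or 42–48% beyond 808.

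**Power.** Exact one-sided Poisson test at 0.05, for a subset of the scenarios:

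| Subject-years | OPC 1.2, true 1.2: reject at ≤ | Power | OPC 1.4, true 1.4: power | OPC 1.4, true 1.5: power |
|---|---|---|---|---|
| 800 | 11 | 74% | 84% | 77% |
| 808 | 11 | 73% | 83% | 76% |
| 1,243 | 20 | 92% | 95% | 91% |
| 1,412 | 24 | 96% | 97% | 94% |
| 1,518 | 26 | 97% | 98% | 96% |

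Integer cut-offs make power uneven; for OPC 1.2 the minimum between 1,243 and 1,518 is 91%, at 1,260. The last column uses the model 6900P late bleeding rate of 1.5 per 100 patient-years (Appendix 9, Table 4). For OPC 2.5 at a true rate of 2.5, power is 98% at 808 and above 99% at full exposure.

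Other test forms change the level but not the gap. For OPC 1.2, the normal and square-root approximations give 78% and 82% at 800, and 94–97% over 1,243–1,518. If the Section 9.1 Z is applied to event counts (an assumption), it rejects at 13 or fewer events at 808, with size 8.4% and power 89%, against 96–98% at full exposure.

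At the model 6900 late rates (thromboembolism 0.7, anticoagulant-related hemorrhage 0.8, perivalvular leak 0.5, endocarditis 0.3), power at 808 is at least 99.7% for every test.

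**Precision.** Near an observed rate of 1.2, the one-sided 95% upper bound is 2.10 at 808 (10 events), 1.86 at 1,243 (15 events) and 1.76 at 1,518 (18 events).

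**Timing.** Counting from November 2013, Section 4.2 expects "another three (3) years before the first patient reaches the 8-year follow-up visit and up to six (6) years to achieve 101 patients", which puts the first 8-year visit around November 2016. Its counts leave 203 subjects in follow-up as stated, or 249 − 55 = 194 by subtraction. Over three years, at the hazards for R = 0.404 to 0.56 with e = 0, these add about 493–547 subject-years. The trigger is then met before November 2016 if 261–315 years had accrued by November 2013, that is 1.0–1.3 years for each of 249 implanted subjects, when the longest follow-up was already 5 years. Under assumed even accrual, 808 falls between about mid-2014 and late 2015. No accrual curve is given, so this is very probable rather than certain.

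**The case against.** The strongest reply is that 808 is plainly meant as a floor. The clause sits in a sample-size section, the derivation says the other subjects' years more than meet the 800 required, Section 9.2 includes all data to explant or death, and Table 2 sets the final report by 8-year completers. This stands as evidence of intent, and makes the full-data reading the likelier one. It does not rescue the sentence, which has no wording such as *at least* and fixes when the rate is computed.

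It is also fair that the clash with Section 9.2 is milder than the clash inside 9.1. A timing rule can still use every enrolled subject and all data collected by that date, so a reader who infers that 808 would exclude subjects goes too far.

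The percentages depend on assumptions. The low end pairs retention that only just meets the target with 9.4% early deaths, although model 6900P had 1.4%; and since 8 years is a minimum follow-up, the cap may understate exposure. The internal inconsistency depends on none of this.

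**Conclusion.** The trigger in Section 9.1 is wrong on the plan's own derivation and should be corrected. Read literally, it would run the long-term safety tests on about 53–65% of expected exposure (808/1,518 to 808/1,243), under the assumptions above. The consequence is wider intervals and forgone power when a true rate is near its OPC; among the documented predecessor rates, that is model 6900P bleeding (76% at 808 against about 91–96%).

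Three stronger conclusions might be inferred, and the documents do not support them:
- *The safety tests are underpowered against the plan's claim.* The 80% is stated for 800 subject-years, 808 exceeds that, and the 78–82% from the usual approximations brackets it.
- *The cut biases the rates.* Under the constant hazard that a linearized rate presumes, it does not, and no hazard shape is given for this cohort.
- *The sponsor intends to discard nearly half the data.* Section 9.2 and Table 2 point the other way.

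**What to change.** In Section 9.1, replace the 808 clause with: *computed at the final analysis (at least 101 subjects with 8-year follow-up) on all subject-years and events in the safety analysis population of Section 9.2, with 800 subject-years as the minimum exposure.*

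This costs one clause and no new data. Descriptive interim reporting is unaffected. Stating the expected exposure, or power for each endpoint, would help readers but is optional. If a cut at 808 total subject-years really is intended, the plan should say why and reconcile it with the 8 × 101 derivation, Section 9.2 and Table 2.
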